# 12.5 Secondary Safety Analysis

The secondary safety analysis relates to the incidence of treatment-emergent adverse events (TEAEs). TEAEs are those with initial onset or increasing in severity after the first dose of study treatment. TEAEs will be graded by the investigator according to the Common Terminology Criteria for Adverse Events (CTCAE) version 5.0 and coded using the Medical Dictionary for Regulatory Activities (MedDRA). The number and percentage of subjects who experienced any AE, serious AE (SAE), treatment-related AE, and treatment-related SAE will be summarized according to worst toxicity grades. The summaries will present AEs both on the entire study period and by cycle (Cycle 1 and Cycles beyond 1) in Cohort 1.

### **Laboratory Test Abnormalities**

The number and percentage of subjects who experienced laboratory test abnormalities will be summarized according to worst toxicity grade observed for each laboratory assay. The analyses will summarize laboratory tests both on the entire study period and by cycle (Cycle 1 and Cycles beyond 1). For laboratory tests without CTCAE grade definitions, results will be categorized as normal, abnormal, or not done.

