# 3.1 Inclusion Criteria

	Prospective Participant Must MATCH ALL these Inclusion Criteria to be Eligible	Yes	No	Supporting Documentation *
1.	History of biopsy-proven ER-positive and/or PR-positive, HER2-negative breast cancer and radiographic evidence of metastatic disease, or locally recurrent unresectable disease. ER-positivity and PR-positivity are defined as ≥ 1% cells staining positive by immunohistochemistry. HER2-negativity is defined by IHC or FISH, per ASCO-CAP 2018 guidelines			
2.	Cancer subtype indicative of alterations to the fibroblast growth factor ligand or receptor (FGF/FGFR alteration): Predicted integrative (IntClust) subtype classification of IC2 or IC6 according classifier on targeted sequencing data from FoundationOne.			

IRB-53650 Version 11 Page 24 of 72 11 November 2021

	Prospective Participant Must MATCH ALL these Inclusion Criteria to be Eligible	Yes	No	Supporting Documentation *
3.	Evaluable or measurable disease.  Cohort 1 only: Evaluable or measurable disease, as defined by RECIST v1.1. Bone-only disease is acceptable.			
4.	≥ 18 years old			
5.	Eastern Cooperative Oncology Group (ECOG) performance status 0 to 2			
6.	Prior cancer therapy (except for endocrine therapy, denosumab, or bisphosphonates) must be discontinued for 2 weeks prior to initiation of study drugs. Recovery from adverse events of previous cancer therapies to baseline or Grade 1 except for alopecia or stable Grade 2 neuropathy. Radiotherapy must also be completed at least 2 weeks prior to initiation of study drugs			
7.	Absolute neutrophil count (ANC) ≥ 1,000/mm 			
8.	Platelets ≥ 75,000/mm 			
9.	Hemoglobin ≥ 9.0 g/dL			
10.	Total bilirubin ≤ 1.8 mg/dL (unless documented Gilbert's disease)			
11.	Aspartate aminotransferase (AST) and alanine aminotransferase (ALT) < 90 U/L			
12.	Estimated glomerular filtration rate (GFR) ≥ 45 mL/min			
13.	Phosphorus between 2.5 and 4.5 mg/dL, inclusive			
14.	Total corrected (for albumin) serum calcium between 8.5 and 10.5 mg/dL, inclusive			
15.	Amylase < 200 U/L			
16.	Lipase < 120 U/L			
17.	Ability to understand and the willingness to sign a written informed consent document			

Prospective Participant Must MATCH ALL these Inclusion Criteria to be Eligible	Yes	No	Supporting Documentation *

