	
 
If ECG assessments show no QTcF ≥ 481 msec, ECG monitoring will be performed at each subsequent visit, per visit schedule for subsequent cycles.
 
					
	
 
If ECG assessments are still abnormal (QTcF ≥ 481 msec and ≤ 500 msec), then ECG monitoring must continue every 2 weeks or as clinically indicated, for all subsequent cycles.
 
					
	
 
Subjects who experience recurrent QTcF ≥ 500msec after one dose reduction will be withdrawn from study.
 
					
	If QTcF > 500 msec or > 60 msec change from the baseline is observed, a plasma sample for determination of infigratinib concentration should be obtained with the time of sample collection noted.					
Grade 4: Torsade de pointes or polymorphic ventricular tachycardia or signs/symptoms of serious arrhythmia	Discontinue infigratinib.  A plasma sample for determination of infigratinib concentration should be obtained with the time of sample collection noted.					
Cardiac Disorders - Others						
Grade ≥ 3 OR Congestive heart failure Grade ≥ 2	Discontinue infigratinib.					
	INVESTIGATIONS-HEMATOLOGY *					
ANC Decreased (Neutropenia)*						
Grade 3 (ANC < 1.0 to 0.5 × 10  /L)	Hold dose of infigratinib until resolved to CTCAE Grade ≤ 2 or baseline, then					
	
 
If resolved within ≤ 7 days, maintain dose level of infigratinib
 
					
	If resolved between > 7 days and 14 days, decrease by     dose level of infigratinib					
	If not resolved within ≤ 14 days, discontinue infigratinib					
Grade 4 (ANC < 0.5 × 10  /L)	Hold dose of infigratinib until resolved to CTCAE ≤ Grade 2, decrease by 1 dose level of infigratinib					
	If not resolved within ≤ 14 days, discontinue infigratinib					

**Table 6.** Criteria for Interruption and Re-initiation of Infigratinib for AEs Considered to be Possibly Related to Infigratinib

Possibly Related to Illigratifie						
Worst Toxicity CTCAE (v5.0) Grade (Unless Otherwise Specified)	Recommended Dose Modifications any Time During a Cycle of Therapy					
of Neutropenia": that is, if any of the present – sepsis syndrome, age > 0	nistering G-CSF per NCCN guidelines (Version 2.2019) "Management be following risk factors for an infection-associated complication are 65 years, ANC < 100/mcL, clinically documented infection, invasive time of fever, or prior episode of febrile neutropenia.					

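### The laboratory table counts worst grade observed with no baseline reference, so an unchanged low-grade abnormality at entry is tabulated as an on-study abnormality

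*Combined protocol and SAP*

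**What the plan says.** The laboratory paragraph of Section 12.5 tabulates the number and percentage of subjects with abnormalities, "summarized according to worst toxicity grade observed for each laboratory assay". It does so for the study as a whole and separately for Cycle 1 and later cycles. For tests without CTCAE grades, "results will be categorized as normal, abnormal, or not done". The paragraph does not define baseline, has no treatment-emergent rule and calls for no shift table. No other section supplies these for laboratory data.

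The adverse event paragraph just before it does refer to the pre-treatment state: "TEAEs are those with initial onset or increasing in severity after the first dose of study treatment". Section 10.2 repeats that definition, again for adverse events only.

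Section 3.1 sets entry limits that allow abnormal values. One is "Hemoglobin ≥ 9.0 g/dL". Others are platelets from 75,000/mm³, ANC from 1,000/mm³, estimated GFR from 45 mL/min, AST and ALT below 90 U/L, and lipase below 120 U/L. Criterion 6 also accepts residual Grade 1 toxicity from earlier therapy.

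**The concern.** A worst-grade count answers what grade was reached. It does not answer whether the value got worse after treatment began. When subjects may enter with mild cytopenia or mildly raised enzymes, the two questions have different answers, and the table as specified reports only the first.

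At stake is how this descriptive table reads. Under Section 7.2, a laboratory value becomes an adverse event only if it causes symptoms, is clinically significant, needs therapy, or changes study drug. For every other laboratory change, the worst-grade table is the only planned summary. The Cycle 1 versus later-cycle comparison is also blurred, because an abnormality that was present at entry and persists appears in both columns.

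**Working it through.** The plan states no figure for this table, so there is none to reproduce. The check is a reading of the rules, followed by simple arithmetic.

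**Step 1. Does an unchanged entry abnormality count?** Take a subject who enters with hemoglobin 9.5 g/dL (an illustrative value) and stays there. The value is eligible under Section 3.1. On-treatment samples are scheduled in Cycle 1 and later (Section 9), and each shows the same low value. The worst grade observed is the entry grade, so the subject is counted overall and in both cycle columns. This holds even if screening values are left out.

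**Step 2. Which grades can be affected?** The entry floors compare with the Grade 3 bands in Table 6 (Section 6) as follows.

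| Assay | Entry floor (3.1) | Grade 3 begins (Table 6) |
|---|---|---|
| ANC | 1.0 × 10⁹/L | below 1.0 × 10⁹/L |
| Hemoglobin | 9.0 g/dL | below 8.0 g/dL |
| Platelets | 75 × 10⁹/L | below 50 × 10⁹/L |

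Every floor lies at or above the Grade 3 boundary. A value unchanged from an eligible entry value can fill only Grade 1–2 cells for these three assays. I assume the local lower limits of normal lie above the floors; the documents do not give them.

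**Step 3. Other assays.** How abnormal the AST/ALT, bilirubin, amylase and lipase entry limits are depends on local upper limits of normal, which are not given. Creatinine grading in Table 6 includes a multiple-of-baseline alternative, so it has some baseline reference, but Section 12.5 does not rely on it. Phosphorus (2.5 to 4.5 mg/dL) and corrected calcium (8.5 to 10.5 mg/dL) are bounded on both sides at entry and are largely spared.

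**Step 4. The Cycle 1 column.** Footnote 6 in Section 9 has on-treatment hematology drawn before dosing. A Cycle 1 Day 1 sample may therefore be labelled Cycle 1 although it precedes any drug. Footnotes 6 to 9 waive that sample if baseline was drawn within 72 hours, so this affects some subjects only.

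**Step 5. Weight of one subject.** The synopsis gives 3 to 12 evaluable subjects. One subject contributes 100/n points: 100/12 = 8.3, 100/6 = 16.7, 100/3 = 33.3. Replaced subjects who took infigratinib stay in the population (Section 12.7) and would lower these weights somewhat.

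**Step 6. Chance that a given assay is touched.** With baseline prevalence b (an assumption; the documents give none), the chance that at least one of n subjects enters abnormal is 1 − (1 − b)ⁿ. For example, 1 − 0.90¹² = 0.718.

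| b | n = 3 | n = 6 | n = 12 |
|---|---|---|---|
| 5% | 14% | 27% | 46% |
| 10% | 27% | 47% | 72% |
| 20% | 49% | 74% | 93% |
| 40% | 78% | 95% | 99.8% |

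**Step 7. Illustration of the gap.** Assume that new abnormalities arise in 10% of those normal at entry and that entry abnormalities persist unchanged. Expected worst-grade incidence is b + (1 − b) × 0.10; new-onset incidence is (1 − b) × 0.10. At b = 10% these are 19% and 9%; at 20%, 28% and 8%; at 40%, 46% and 6%. The gap equals b.

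**The case against.** The strongest reply is that the plan is silent and does not state a wrong rule. It speaks of subjects who experienced abnormalities, which may be meant as new onset, and it does not say whether screening values belong to the study period. The adverse event paragraph also uses worst grade, by period and by cycle, so the laboratory paragraph only mirrors that format for another type of data. The study is descriptive and small, and counting only worsened grades is one convention among several.

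Part of this stands. The two paragraphs do not contradict each other, and whether screening values are included is open. The silence does not remove the problem, though: a persisting abnormality is observed on treatment whichever way screening values are handled, and nothing in the text tells the programmer to exclude it.

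A reader might infer that the trial's toxicity results are inflated. The documents do not support that. Laboratory values that qualify as adverse events pass through the onset-or-worsening definition (Sections 10.2 and 12.5), and conditions present at consent go to medical history (Section 7.3). DLTs have their own criteria and a relatedness requirement (Section 10.1, Table 7). The laboratory table is not an objective, an endpoint or a registry outcome, and it plays no part in the dose decisions of Section 12.4.

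**Conclusion.** The point holds as a minor weakness in a supporting descriptive table. As written, unchanged entry abnormalities are tabulated as on-study laboratory abnormalities. The table can therefore overstate Grade 1–2 hematology findings, and possibly hepatic, pancreatic or renal ones, and it cannot tell pre-existing values from new ones.

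Each affected subject moves an assay's incidence by 8.3 to 33.3 points across the planned sample sizes. How many subjects are affected cannot be derived from the documents, and the prevalences used above are assumptions. It would go too far to say that some stated share of subjects will be miscounted. It would also go too far to say that Grade 3–4 neutrophil, hemoglobin or platelet counts are filled by unchanged entry values, because the entry floors rule that out.

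**What to change.** In Section 12.5:

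- Define baseline as the last value before the first dose of study treatment.
- Restrict the on-treatment summary, including the Cycle 1 column, to values taken after the first dose.
- For each graded assay, present a shift table of baseline grade by worst on-treatment grade. For ungraded assays, show the shift from normal to abnormal.
- Report treatment-emergent laboratory abnormalities as worsening of at least one grade from baseline.

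The baseline and on-treatment laboratory tests are already in the Section 9 calendar, so no new samples, visits or subjects are needed. The cost is table programming and inclusion in a protocol or SAP modification; a protocol change needs IRB approval under Section 11.1, so it is best combined with the next one.

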## 12.6 Efficacy Analysis

Tumor response will be presented in the form of subject data listings that include, but are not limited to:

- The classified integrative subtype (IC2 or IC6)
- Received (maximum) dose
- Overall tumor response at each imaging assessment point
- Best overall response

In addition, disease progression date, death date, date of first response, and last tumor assessment date will be listed, together with progression-free survival. A Kaplan-Meier plot will be created for progression-free survival overall, for IC2-classified tumors separately, and for IC6-classified tumors separately.

# 12.7 Analysis Population

All subjects who received at least one dose of the study drug (infigratinib) will be analyzed for the safety and efficacy outcomes outlined in sections 12.4; 12.5; and 12.6.

#### 12.8 Accrual Considerations

There are approximately 600 new breast cancer patients seen annually at the Stanford Cancer Institute, an estimated 50 percent metastatic and 60% HR-positive, HER2-negative. Based on METABRIC, we estimate that approximately 5% of HR-positive, HER2-negative tumors are integrative subtype 2 and 5% are integrative subtype 6.  We thus anticipate approximately 20 eligible subjects per year, adequate for the accrual goals. If accrual unexpectedly falls short, additional clinical sites may be added to the study.

### 12.9 Criteria for future studies

If an MTD for infigratinib in combination with tamoxifen is identified with an acceptable number of DLTs (see Section 12.4), the combination will be deemed acceptable for future studies in this biomarker-selected population of advanced breast cancer. Should this combination prove safe, the study team is planning additional studies to assess efficacy in multiple populations of breast cancer subjects whose tumors harbor FGFR pathway alterations.

### **APPENDICES**

# APPENDIX A: List of prohibited medications and substances

Category	Drug Names	
Strong inhibitors of CYP3A4	clarithromycin, conivaptan, fluconazole, fluvoxamine, indinavir, itraconazole, ketoconazole, lopinavir, mibefradil, miconazole, nefazodone, nelfinavir, norfloxacin, posaconazole, ritonavir, saquinavir, telithromycin, voriconazole	
	grapefruit, grapefruit juice, grapefruit hybrids, pomegranates, star fruits, pomelos, Seville oranges or products containing juice of these fruits	
Strong inducers of CYP3A4	avasimibe, carbamazepine, nevirapine, phenobarbital, phenytoin, pioglitazone, primidone, rifabutin, rifampin, St. John's wort, troglitazone	
Medications which increase serum phosphorus and/or calcium	calcium, parathyroid hormone, phosphate, vitamin D (including multivitamins containing vitamin D)	
Medications with established potential for QT prolongation or TdP	amiodarone, anagrelide, arsenic trioxide, astemizole (off US market), azithromycin, bepridil (off US market), chloroquine, chlorpromazine, cisapride (off US market), citalopram, clarithromycin, cocaine, disopyramide, dofetilide, domperidone (not on US market), dronedarone, droperidol, erythromycin, escitalopram, flecainide, halofantrine, haloperidol, ibutilide, levofloxacin, levomethadyl (off US market), mesoridazine (off US market), methadone, moxifloxacin, pentamidine, pimozide, probucol (off US market), procainamide (oral off US market), quinidine, sevoflurane, sotalol, sparfloxacin (off US market), sulpiride (not on US market), terfenadine (off US market), thioridazine, vandetanib	

Abbreviations: CYP – cytochrome P; TdP – Torsades de Pointes; US – United States.

APPENDIX B: List of drugs to be used with caution while on study

Category	Drug Names		
CYP3A substrates with narrow therapeutic index	alfentanil, cyclosporine, diergotamine, dihydroergotamine, ergotamine, fentanyl, sirolimus, tacrolimus, terfenadine, warfarin sodium or any other coumadin-derivative anticoagulants, direct thrombin inhibitors (eg, argatroban), and Factor Xa inhibitors (eg, rivaroxaban)		
Moderate inhibitors of CYP3A4	amprenavir, aprepitant, atazanavir, cannabinoids, casopitant, cimetidine, ciprofloxacin, darunavir, diltiazem, fosamprenavir, imatinib, metronidazole, Schisandra sphenanthera, sertraline, suboxone, tofisopam, verapamil, zafirlukast		
Moderate inducers of CYP3A4	bosentan, cotrimoxazole, efavirenz, etravirine, ethosuximide, genistein, metyrapone, mexiletine, modafinil, nafcillin, talviraline, tipranavir		
Medications which alter the pH of the GI tract a,b	antacids, H₂antagonists (eg, ranitidine), proton-pump inhibitors (eg, omeprazole)		
Medications that have possible risk of TdP/QT prolongation	alfuzosin, amantadine, atazanavir, chloral hydrate, clozapine, dolasetron, eribulin, famotidine, felbamate, fingolimod, foscarnet, fosphenytoin, gatifloxacin, gemifloxacin, granisertron, iloperidone, indapamide, isradipine, lapatinib, lithium, moexipril, nicardipine, nilotinib, octreotide, ofloxacin, ondansetron, oxytocin, paliperidone, pasireotide, quetiapine, ranolazine, risperidone, roxithromycin, sertindole, sunitinib, tamoxifen, tizanidine, vardenafil, venlafaxine, ziprasidone		
Medications that have conditional risk of TdP/QT prolongation	amitriptyline, amisulpride, ciprofloxacin, clomipramine, desipramine, diphenhydramine, doxepin, fluoxetine, galantamine, imipramine, nortriptyline, paroxetine, protriptyline, sertraline, solifenacin, trazodone, trimethoprim-sulfa, trimipramine		
BCRP substrates	atorvastatin, irinotecan, methotrexate, rosuvastatin, simvastatin, sulfasalazine, topotecan		

Abbreviations: BCRP, breast cancer resistance protein; CYP, cytochrome p; F DA, Food and Drug Administration; GI, gastrointestinal; TdP, Torsades de Pointes

<sup>a Infigratinib should be dosed at least 2 hours before or 10 hours after dosing with a gastric protection agent.

b If possible, proton pump inhibitors should be avoided due to their long pharmacodynamic effect and replaced with H2 antagonists or antacids.

### **APPENDIX C: RECIST v1.1**

### **Measurable Lesions**

- Lesions that can be accurately measured in at least one dimension.
- Lesions with longest diameter twice the slice thickness and at least 10 mm or greater when assessed by CT or MRI (slice thickness 5 to 8 mm).
- Superficial lesions with longest diameter 10 mm or greater when assessed by caliper.
- Malignant lymph nodes with the short axis 15 mm or greater when assessed by CT.

NOTE: The shortest axis is used as the diameter for malignant lymph nodes, longest axis for all other measurable lesions.

#### Non-measurable disease

Non-measurable disease includes lesions too small to be considered measurable (including nodes with short axis between 10 and 14.9 mm) and truly non-measurable disease such as pleural or pericardial effusions, ascites, inflammatory breast disease, leptomeningeal disease, lymphangitic involvement of skin or lung, clinical lesions that cannot be accurately measured with calipers, abdominal masses identified by physical exam that are not measurable by reproducible imaging techniques.

- Bone disease: Bone disease is non-measurable with the exception of soft tissue components that can be evaluated by CT or MRI and meet the definition of measurability at baseline.
- Previous local treatment: A previously irradiated lesion (or lesion subjected to other local treatment) is non-measurable unless it has progressed since completion of treatment.

#### **Normal sites**

- Cystic lesions: Simple cysts should not be considered as malignant lesions and should not be recorded either as target or non-target disease. Cystic lesions thought to represent cystic metastases can be measurable lesions, if they meet the specific definition above.
   If non-cystic lesions are also present, these are preferred as target lesions.
- Normal nodes: Nodes with short axis < 10 mm are considered normal and should not be recorded or followed either as measurable or non-measurable disease.

#### RECORDING TUMOR ASSESSMENTS

All sites of disease must be assessed at baseline. Baseline assessments should be done as close as possible prior to study start. For an adequate baseline assessment, all required scans must be done within 28 days prior to treatment and all disease must be documented appropriately. If baseline assessment is inadequate, subsequent statuses generally should be indeterminate.

#### **Target lesions**

All measurable lesions up to a maximum of 2 lesions per organ, 5 lesions in total, representative of all involved organs, should be identified as target lesions at baseline. Target lesions should

be selected on the basis of size (longest lesions) and suitability for accurate repeated measurements. Record the longest diameter for each lesion, except in the case of pathological lymph nodes for which the short axis should be recorded. The sum of the diameters (longest for non-nodal lesions, short axis for nodal lesions) for all target lesions at baseline will be the basis for comparison to assessments performed on study.

- If two target lesions coalesce, the measurement of the coalesced mass is used. If a large target lesion splits, the sum of the parts is used.
- Measurements for target lesions that become small should continue to be recorded. If a
  target lesion becomes too small to measure, 0 mm should be recorded if the lesion is
  considered to have disappeared; otherwise, a default value of 5 mm should be recorded.

NOTE: When nodal lesions decrease to < 10 mm (normal), the actual measurement should still be recorded.

### Non-target disease

All non-measurable disease is non-target. All measurable lesions not identified as target lesions are also included as non-target disease. Measurements are not required but rather assessments will be expressed as ABSENT, INDETERMINATE, PRESENT/NOT INCREASED, INCREASED. Multiple non-target lesions in one organ may be recorded as a single item on the case report form (eg, 'multiple enlarged pelvic lymph nodes' or 'multiple liver metastases').

#### **OBJECTIVE RESPONSE STATUS AT EACH EVALUATION.**

Disease sites must be assessed using the same technique as baseline, including consistent administration of contrast and timing of scanning. If a change needs to be made the case must be discussed with the radiologist to determine if substitution is possible. If not, subsequent objective statuses are indeterminate.

